7.3.2.14. Major investigation items

Hepatotoxicity should be evaluated in this study as a major investigation item and, if information on hepatotoxicity is obtained, it will be separately investigated in detail.

[Rationale for setting]

Although necrosis and hypertrophy of hepatocytes were observed in the repeated-dose toxicity study in mice, since the Japanese clinical data at the time of approval application are limited, hepatotoxicity was set as the major investigation item in this study to confirm the post-marketing safety profile.

7.3.2.15. Confirmation of description concerning adverse events corresponding to major investigation item

The investigator will confirm that the AEs corresponding to hepatotoxicity, the major investigation item in this study, have been entered in the AE column.

7.4. Data sources

In this study, the investigators extract the necessary information from the medical record in accordance with the full protocol.

7.5. Study size

7.5.1. Planned sample size

All patients who received/used this drug will be targeted in this study.

7.5.2. Rationale for sample size

On the basis of the review of data on patients with familial amyloid polyneuropathy who were registered in the database from the Amyloidosis Clinical Survey Forms of the Specific Diseases Treatment Research Program by the Ministry of Health, Labour and Welfare for 3 years from 2003 to 2005, it is reported that the number of patients with familial amyloid polyneuropathy is 64 to 88 patients/year, and the estimated prevalence of familial amyloid polyneuropathy in Japan is 0.87 to 1.1 per population of 1 million people after the number of patients was corrected and calculated from the acquisition rate of data¹⁾. When this prevalence is multiplied by the Japanese population (127.54 million, as of November 2012), the estimated number of patients with TTR-FAP (hereinafter referred to as this disease) is approximately 111 to 140. On the website of the Japan Intractable Diseases Information Center, the estimated annual number of patients treated for this disease is approximately 130 on the basis of the nationwide epidemiological survey conducted in 1991. As described above, considering that this disease is a rare disease and the safety and efficacy information of this drug based on Japanese clinical studies are limited, all patients who received/used this drug will be collected as much as possible.

7.6. Data management

7.6.1. Case report forms (CRFs)/ Electronic data record

As used in this protocol, the term CRF should be understood to refer to a paper form, depending on the data collection method used in this study. A CRF is required and should be completed for each included patient. The completed original CRFs are the sole property of Pfizer and should not be made available in any form to third parties, except for authorized representatives of Pfizer or appropriate regulatory authorities, without written permission from Pfizer. The investigator shall ensure that the CRFs are securely stored at the study site in paper form and will be secured in a locked room to prevent access by unauthorized third parties.

The investigator has ultimate responsibility for the collection and reporting of all clinical, safety, and laboratory data entered on the CRFs and any other data collection forms (source documents) and ensuring that they are accurate, authentic/original, attributable, complete, consistent, legible, timely (contemporaneous), enduring, and available when required. The CRFs must be signed by the investigator or by an authorized staff member to attest that the data contained on the CRFs are true. Any corrections to entries made in the CRFs or source documents must be dated, initialed (or stamped "correction seal"), and explained (if necessary) and should not obscure the original entry.

The source documents are the hospital or the physician's chart. In these cases, data collected on the CRFs must match those charts.

7.6.2. Record retention

The records related to this study should be retained at the study site until the End of Study Letter by Pfizer is received or during the period defined by the study site, whichever is longer.

7.6.3. Data collection method

Registration and study data for this study will be collected and recorded in the registration form and CRFs to be supplied by Pfizer. Investigator will complete (each volume of forms) promptly after (each) observation period and submit them to Pfizer.

7.6.4. Patient registration

7.6.4.1. Procedure of patient registration

The investigator will complete the designated registration form provided by Pfizer after the start of treatment with this drug and send it to Patient Registration Center via FAX.

[Patient Registration Center]

FAX: **PPD** (Available 24 Hours) Business hours: 9:00 to 17:00 on Mondays through Fridays [except for national holidays, and New Year holidays (29 December to 4 January)]

- 1. After the end of patient registration, a "registration confirmation sheet" will be sent by FAX from Patient Registration Center to the investigator.
- 2. If there is something to be confirmed found in the registration form, confirmation will be requested with the investigator. In the case of confirmation, "request form of confirmation" and "registration form (copy)" will be sent from the registration center to the investigator by [contact]. Confirmation of patients registered

During the registration period, Pfizer will confirm with the investigator that all patients have been registered at the study sites conducting the study every year using an "all-cases survey confirmation sheet".

7.6.5. Reminders concerning completing, revising, and submission of case report form 7.6.5.1. Completing

The investigator will check the study items and complete the CRFs based on consultation records and medical records including the results of various tests using indelible ink such as ballpoint pen.

7.6.5.2. Revising

Upon receiving Pfizer's inquiry on the contents of the CRF (query forms), the investigator will again confirm the contents of consultation records, and as required, correct relevant sections of the CRF and submit it.

7.6.5.3. Confirming

After the entry and revision of the CRFs (or CRFs for resurvey) are fully completed, the investigator will confirm any inadequacies in the study items again and affix the printed name and seal or sign the CRFs.

7.6.5.4. Submitting

The investigator will promptly submit the CRFs to Pfizer upon completion.

7.7. Data analysis

1. Definition of analysis set

The safety analysis set (SAS) consists of all patients who received this drug at least once. The effectiveness analysis set consists of those for whom the effectiveness evaluation was conducted at least once among the SAS. The details will be described in the separately prescribed Statistical Analysis Plan (SAP).

2. Method of analysis

(1) Major analysis for safety evaluation

The occurrence of ADRs and the incidence of ADRs (percentage of patients with AEs for which the causal relationship with this drug cannot be ruled out) will be calculated in the SAS.

(2) Major analysis for effectiveness evaluation

For NIS, QOL-DN, and mBMI, their values and changes from baseline at each time point will be calculated in the effectiveness evaluation set. For ambulatory status, motor function (MRC), tendon reflex, tactile sense, pain sensation, vibration sense, and positional sense, changes from baseline at each time point will be calculated. In addition, survival time analysis will be performed using survival information obtained up to 3 years after the start of treatment.

Detailed methodology for summary and statistical analyses of data collected in this study will be documented in a SAP, which will be dated, filed and maintained by Pfizer. The SAP may modify the plans outlined in the protocol; any major modifications of primary endpoint definitions or their analyses would be reflected in a protocol amendment.

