7.2.2. Duration of study

The planned period covered by this study is as follows.

Duration of study: November 2013 to May 2021 (7.5 years)

Registration period: November 2013 to November 2019 (6 years)

A contract will be concluded after the start date of the study period, and then, the patient registration will be started. The transition to registration only after the registration period will be implemented after consultation with the Pharmaceuticals and Medical Devices Agency (PMDA).

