7.2.4. Observation period

3 years from the first day of treatment with this drug (156 weeks) However, the observation period for patients who started to receive this drug after May 2018 will be 1.5 years (78 weeks).

> Pfizer Confidential Page 12 of 37

If the treatment with this drug is discontinued during the observation period, the observation period will be until the day of discontinuation. If the dose of this drug is changed for the treatment of ATTR-CM, the observation period will be up to the date of last dose of 20 mg.

This study will be conducted using booklet type CRF.

The safety and efficacy assessments will be performed at the first visit (including the end date of the observation period) on or after the end date of the observation period (day of discontinuation if the treatment is discontinued during the observation period or date of the last dose of 20 mg if the dose was changed for the treatment of ATTR-CM). However, if a subject is lost to follow-up halfway through, the safety and efficacy assessments will be performed using the information on the last visit date.

Booklet No.	Observation period	
Booklet 1	First day of treatment to Week 78 (1.5 years)	
Booklet 2	Week 79 to Week 156 (3 years)	

7.3. Registration items and study items This study will be conducted according to the following schedule of observation.

Table 1. Schedule of observation

			Booklet 1		Book	det 2
Item	Registr ation form	At start of the study	Week 52 (1 year)	Week 78 (1.5 years)	Week 104 (2 years)	Week 156 (3 years)
Information to identify the subject			-	-	-	-
First day of treatment with this drug			-	-	-	-
Presence or absence of having received/used this drug at other sites, and if Yes, patient's duration of treatment	•					
THAOS registration status/THAOS registration ID						
State of concurrent medical examination	-					→
Background variables	-		-	-	-	-
History of previous treatment drugs for the targeted disease	-	•	-	-	-	-
Targeted drug use record	-	•				>
Concomitant therapy (drug therapy/ non-drug therapy)	-	•				
General tests (height, body weight, pulse, blood pressure)	-	•				
Clinical laboratory tests	-	•				→
Plasma concentration of tafamidis (to be performed only for patients with severe hepatic impairment)	-					•
Cardiovascular evaluation (ECG, echocardiography)	-					
Assessment of neurological function (NIS)	-		-		-	
Quality of Life (QOL-DN)	-		-		-	
Ambulatory state	-		-		-	

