## 2.1. Study design

Target patients

All patients who received/used this drug will be targeted in this study.

Dosage and administration

The usual adult dosage for oral use is 20 mg of tafamidis meglumine once daily.

Observation period

3 years from the first day of treatment with this drug (156 weeks)

However, the observation period for patients who started to receive this drug after May 2018 will be 1.5 years (78 weeks).

Major investigation items

Hepatotoxicity should be evaluated in this study as a major investigation item and, if information on hepatotoxicity is obtained, it will be separately investigated in detail.

[Rationale for setting]

Although necrosis and hypertrophy of hepatocytes were observed in the repeated-dose toxicity study in mice, since the Japanese clinical data at the time of approval application are limited, hepatotoxicity was set as the major investigation item in this study to confirm the post-marketing safety profile.

Study size and its rationale

[Planned sample size]

All patients who received/used this drug will be targeted in this study.

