#### 8.1.3. Binary variables

For binary variables, patients falling into each binary category will be summarized in terms of n and proportion. When a confidence interval (CI) is determined for a proportion, the two-sided 95% CI (exact method) will be determined.

When a comparison for proportion is made between subgroups, the risk ratio (RR) and its 95% CI will be presented.

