#### 8.2.3.1. Adverse reactions

#### All adverse reactions

Adverse reactions will be summarized by SOC and PT in terms of n and proportion.

In particular, important potential risks, i.e., events related to hepatotoxicity, hypersensitivity reaction, developmental and reproductive toxicity, and infections will be summarized for each event in terms of n and proportion; when n is very small for each event, however, only a listing will be presented in tabular form.

In addition, each of events related to pain in extremity, myalgia, gastrointestinal symptoms, skin, central nervous system, fall, suicide, hepatopathy, thyroid function, vitamin A deficiency, and increased blood glucose will be summarized separately in terms of n and proportion, as necessary.

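### The headline adverse-reaction percentage and its subgroup risk ratios are crude figures over follow-up that is unequal by design, so they refer to no defined time horizon

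*Protocol*

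**What the plan says.** **Main safety measure.** Protocol 7.7 defines it as "the incidence of ADRs (percentage of patients with AEs for which the causal relationship with this drug cannot be ruled out", calculated in the safety analysis set with no time horizon. SAP 8.2.3.1 carries this through: "Adverse reactions will be summarized by SOC and PT in terms of n and proportion". Hepatotoxicity, the major investigation item, is summarised in the same way.

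**Observation.** Protocol 7.2.4 sets "3 years from the first day of treatment with this drug (156 weeks" as the standard. For late starters, SAP 2.1 says that "the observation period for patients who started to receive this drug after May 2018 will be 1.5 years (78 weeks". Protocol 7.2.4 adds: "If the treatment with this drug is discontinued during the observation period, the observation period will be until the day of discontinuation". A dose change for ATTR-CM also closes observation, at the last 20 mg dose.

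**Subgroups.** SAP 8.2.3.3 tabulates the proportion with at least one reaction for each factor in SAP 5.4 and applies SAP 8.1.3: "When a comparison for proportion is made between subgroups, the risk ratio (RR) and its 95% CI will be presented". Duration of treatment is one of those factors. SAP 6.4 names no covariates.

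**What the plan does with time.**
- The onset-timing table in SAP 8.2.3.1 gives counts and proportions by SOC and PT in bands that break at 78 and 156 weeks. Each band has its own denominator of treated patients.
- SAP 8.2.1 counts the safety set by planned observation time, but does not split reaction incidence that way.
- SAP 8.1.5 defines Kaplan-Meier methods. The visible text applies them to survival, not to adverse reactions.
- Protocol 7.9 does not list unequal follow-up among the limitations.

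**The concern.** The study exists to describe safety in long-term use, and its final analysis supports reexamination. A single percentage that mixes patients watched for 78 weeks, patients watched for 156 weeks and patients watched until they stopped does not answer how many patients react within a stated time. It also cannot be set directly beside a figure from another source with a different follow-up mix.

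A risk ratio built from such percentages compares two things at once: the hazard in each subgroup and the time each subgroup was observed. If the time differs, a ratio away from 1 can appear with no difference in hazard. The planned confidence interval covers sampling error only and would not show this.

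**Working it through.** **The plan's own figure.** The only calculated figure is the estimated number of patients (Protocol 7.5.2): 0.87 × 127.54 = 110.96 and 1.1 × 127.54 = 140.29, matching the stated 111 to 140. The plan gives no expected reaction rate, so every rate below is an assumption.

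**Inputs**
- Planned observation of 156 or 78 weeks (Protocol 7.2.4).
- Share *f* on 78 weeks: not given. Protocol 7.2.2 states "Registration period: November 2013 to November 2019 (6 years", which is 72 months, of which about 18 fall after May 2018. Uniform entry would give 18/72 = 25%. I vary *f* from 10% to 40%.
- Three-year risk of a first reaction, R(156): not given. I take 30% for illustration and 10% to 50% as a range.
- Hazard shape: constant, or front-loaded (Weibull, shape 0.5).

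**Step 1. Risk at 78 weeks when R(156) = 30%.** The cumulative hazard at 156 weeks is −ln(0.7) = 0.357.
- Constant: 1 − exp(−0.357 × 0.5) = 16.3%.
- Front-loaded: 1 − exp(−0.357 × √0.5) = 22.3%.

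**Step 2. Expected crude percentage** = (1 − f) × R(156) + f × R(78). With f = 25%:
- Constant: 0.75 × 30 + 0.25 × 16.3 = 26.6%.
- Front-loaded: 0.75 × 30 + 0.25 × 22.3 = 28.1%.

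Relative shortfall against the 3-year risk, for R(156) from 10% to 50%:

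| Share on 78 weeks | Constant hazard | Front-loaded hazard |
|---|---|---|
| 10% | 4–5% | 2–3% |
| 25% | 10–12% | 6–7% |
| 40% | 17–20% | 9–11% |

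**Step 3. Add discontinuation.** Assume stopping is exponential and independent of reactions, with hazard g, and reactions have constant hazard h. The proportion with a reaction by time t is h/(h+g) × [1 − exp(−(h+g)t)]. With 20% stopping over 3 years, h = 0.357/3 = 0.119 and g = −ln(0.8)/3 = 0.074 per year.
- At 3 years: 27.1%. This is discontinuation alone (f = 0), a loss of about the same size as the 78-week rule.
- At 1.5 years: 15.5%.
- Mixed at f = 25%: 0.75 × 27.1 + 0.25 × 15.5 = 24.2%.

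A simulation of this case (n = 130, 5,000 runs) gave a mean crude figure of 24.3%, a Kaplan-Meier 3-year risk of 30.1%, and a rate of 12.0 per 100 patient-years against a true 11.9.

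**Step 4. Subgroup risk ratio with no true difference**, R(156) = 30%, no discontinuation:

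| Share on 78 weeks, subgroup v reference | Constant | Front-loaded |
|---|---|---|
| 25% v 25% | 1.00 | 1.00 |
| 35% v 15% | 0.90 | 0.95 |
| 40% v 10% | 0.86 | 0.92 |
| 100% v 0% (extreme) | 0.54 | 0.74 |

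For example, 40% v 10% under a constant hazard is (0.6 × 30 + 0.4 × 16.3)/(0.9 × 30 + 0.1 × 16.3) = 24.5/28.6 = 0.86.

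**Step 5. The duration-of-treatment factor.** Here category and time observed are tied by definition. SAP 8.2.2 also assigns a value above 156 weeks to anyone still treated when observation ends, with no exception for late starters. A late starter still on drug at Week 78 would therefore enter the longest category after half the observation time of the others there.

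**The case against.** **The onset-timing table already deals with time.** This is the strongest reply. The table does more than count: its band-specific denominators mean that patients planned for 78 weeks need not dilute the later bands. That stands. What remains is that it gives no overall cumulative incidence and leaves the risk ratios as they are.

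**The plan never claims a 3-year risk.** Correct. A reader might infer that the planned percentage is a biased estimate of 3-year risk. The documents set no horizon and no hypothesis, so the shortfall exists only if the figure is read that way.

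**Subgroup distortion is not shown.** A reader might infer that the ratios are confounded in general, or take 0.54 as typical. The documents do not support either reading. No factor in SAP 5.4 is defined by start date, an equal mix leaves the null ratio at 1.00, and 0.54 needs every patient in one subgroup and none in the other to be on 78 weeks.

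**Early stoppers need not look safer.** Also correct. Some patients stop because of an adverse event, which the plan records and tabulates, and this can raise the crude percentage among them. Step 3 assumes independence and does not capture it. Records linked across sites (SAP 8.2.1) can also run past 156 weeks, which works the other way and is not modelled.

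**The size is uncertain and modest.** Entry was probably not uniform in an all-patient survey that began soon after approval and includes retrospective cases, so the share on 78 weeks may be below 25%. At an assumed n of 130, the exact 95% interval for 39/130 is 22.3% to 38.7%, wider than the shortfall at f = 25%. That is a fair reason not to overstate the point, but the shortfall is systematic and the interval does not reflect it.

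**Conclusion.** The point holds in a limited form. In the visible text, the headline incidence and the subgroup ratios are crude proportions over unequal observation, with no person-time, cumulative incidence or stratification for adverse reactions.

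If the percentage is read as a 3-year risk, an assumed 30% appears as about 26.6% (constant hazard) or 28.1% (front-loaded) with 25% of patients on 78 weeks, and as 24.2% if 20% also discontinue independently under a constant hazard. Distortion of subgroup ratios is possible rather than established, except for duration of treatment, where the link is built in and the coding rule makes it worse.

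This is a worthwhile low-cost improvement and does not invalidate the planned tables. Part of the SAP is redacted, including a block just after the safety subgroup section, so absence can be asserted only for the visible text.

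**What to change.** Keep the crude percentage. For all adverse reactions and for hepatotoxicity, add:

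1. The cumulative incidence (or Kaplan-Meier estimate) of the first event at Weeks 78 and 156.
2. The rate per 100 patient-years, with time at risk running from first dose to first event or end of observation, computed from dates. The treatment weeks in SAP 8.2.2 are not a substitute: they leave out non-dosing periods and do not stop at the first reaction. The value above 156 weeks should not be used either.

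In SAP 8.2.3.3, stratify the comparisons by planned observation time, restrict them to the first 78 weeks, or use rate ratios. The first two equalise planned time only; rate ratios also allow for early stopping.

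Reconcile the duration coding in SAP 8.2.2 with the 78-week group, and add unequal follow-up to Protocol 7.9.

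**Cost.** Some programming and extra table columns. Treatment and event-onset dates are already collected (Protocol 7.3.2.6 and 7.3.2.12), so no new data are needed. The patient-year rate assumes a roughly constant hazard, which is why the estimates at fixed weeks should stand beside it.

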7.8. Quality control

The site staff will explain the contents of the protocol, etc. to the investigator prior to the implementation of this study and ask the investigator to prepare a CRF based on medical charts

7.9. Limitations of the research methods

The following matters are considered for this study:

- 1. Since no control group is set in the study, there is a limit to the judgment on whether or not a risk of developing AEs and adverse reactions increases due to the administration of the study drug.
- 2. The consideration for confounding factors may not be adequate because the background information may not be sufficiently obtained.
- 3. Since this is a study that collects the information described in medical charts, the set data may not be collected or there may be missing information.

7.10. Other aspects

N/A

8. PROTECTION OF HUMAN SUBJECTS

8.1. Patient information

All parties will comply with all applicable laws, including laws regarding the implementation of organizational and technical measures to ensure protection of patient personal data. Such measures will include omitting patient names or other directly identifiable data in any reports, publications, or other disclosures, except where required by applicable laws. The personal data will be stored at the study site in encrypted electronic and/or paper form and will be password protected or secured in a locked room to ensure that only authorized study staff have access. The study site will implement appropriate technical and organizational measures to ensure that the personal data can be recovered in the event of disaster. In the event of a potential personal data breach, the study site shall be responsible for determining whether a personal data breach has in fact occurred and, if so, providing breach notifications as required by law. To protect the rights and freedoms of natural persons with regard to the processing of personal data, when study data are compiled for transfer to Pfizer and other authorized parties, patient (subject) names will be removed and will be replaced by a single, specific, numerical code, in accordance with a numbering system defined by Pfizer. All other identifiable data transferred to Pfizer or other authorized parties will be identified by this single, patient-specific code. The study site will maintain a confidential list of patients who participated in the study, linking each patient's numerical code to his or her actual identity. In case of data transfer, Pfizer will maintain high standards of confidentiality and protection of patients' personal data consistent with the clinical study agreement and applicable privacy laws.

